- Have contraindication to NRT (past month myocardial infarction, history of serious arrhythmias/or unstable angina pectoris, dermatological disorder),⁶³
- Currently being treated for a psychiatric condition.
- Currently being treated for smoking cessation, alcoholism, or illicit drug use

5) Procedures Involved*

Aim 1: The Clinical Trial

We will be provided with a list of potentially eligible participants including their names, contact information, smoking status, most recent HIV-1 viral load (VL), CD4 count, ART regimen history (e.g., time since first starting ART, current prescription) from the UM HIV Registry (pls. see LOS from [name]; their IRB # is pending approval of this protocol). This will include HIV Registry participants who have previously given consent to be contacted for future research studies. Eligible participants will be contacted by phone and invited to participate in the study. Those who are interested will be screened. Those who are eligible will be scheduled to attend the orientation session. Those who are not eligible, or decline to participate will be encouraged to quit smoking and given a list of available resources. We will additionally recruit participants at HIV community health centers in Miami. The process here will be the same, where interested participants will be screened for eligibility and scheduled for an orientation session.

Breath carbon monoxide (CO) (for cotinine analysis) will be collected at baseline for participants to confirm their smoking status. The breath sample will be collected with a portable CO monitor (Micro COTM by Micro Direct, Inc.). Cut-offs of < 8 ppm for CO

Clinical Trials Registration #: NCT03999411

Date: 6/29/20

and <10 ng/ml for cotinine will be used to determine smoking status (Benowitz et al 2002).

Participants will be assigned to blocks, based on gender. Then, within each block, participants will be randomly assigned to one of three treatment arms:

- 1. Usual Care (UC)/control: Participants in this group will receive a brief advice to adhere to ART, a brief advice to quit smoking, 6-week supplies of NRT, and self-help materials to quit smoking and adhere to ART.

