3. The combined intervention (Crave-to-Quit + emocha apps): In addition to the intervention in the second group, participants in this group will be instructed during the *Orientation Session* to download on their phone the *emocha app* and will receive a tutorial explaining the app content and features. The study team will explain to participants that the app will help them in tracking dose-by-dose medication adherence by recording a video for themselves taking their medication. Participants will be instructed to find a private place to take their medication, make sure their face is well lit when recording, have a clear glass of water, state their name, the date, and each medication as they take it, display their medication pills, show medication in the mouth before swallowing, drink water, show open mouth after swallowing, and repeat the same procedure every time they take the medication. During the 3-month trial, our staff will have full access to the app's web portal to navigate and collect information about patients' adherence to ART (pls. see LOS from emocha Mobile Health Inc.).

At the orientation session, participants will complete a baseline assessment consisting of:

- Demographics and HIV history. Age, race/ethnicity, sexual orientation, relationship status, education, employment, income, time since HIV diagnosis, and HIV 1 RNA VL (from medical chart), ART regimen history, time since first starting ART, current ART prescription, 72 VAS for adherence to ART. 61,62
- *Smoking*. Smoking history, past quit attempt, motivation to quit, confidence in quitting, Fagerström test for nicotine dependence, 73 12-item smoking self-efficacy to resist urge to smoke, 74 and 15-item Minnesota nicotine withdrawal scale (i.e., craving, irritability, anxiety, depression). 75

Clinical Trials Registration #: NCT03999411

Date: 6/29/20

Mindfulness skills: The five facet MT questionnaire that measures MT skills related to observing, describing, acting with awareness, non-judging of inner experience, and non-reactivity to inner experience.⁷⁶

• Others. The 10-item Centers for the Epidemiologic Study of Depression (CES-D) scale, 77 social support, 78 quality of life, 79 and alcohol and substance use (ASSIST). 80

Participants will receive \$50 for completing the baseline assessment.

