Aim 2. Post-intervention Process Evaluation

After the intervention, in-person semi-structured post-intervention evaluation interviews will be conducted with participants from the "Crave-to-quit + emocha" and "only crave-to-quit" groups to further inform our assessment of acceptability and perceived helpfulness of interventions, and identifying key areas for refining the intervention protocols (e.g., improving access, content, usability). Participants will receive a \$50 incentive for participating. This interview will be audio-recorded and transcribed and may take place the same day of the 3-month follow up visit or on a separate date.

6) Data and Specimen Banking*

7) Data Management*

Participant paper assessments will be stored in a locked filing cabinet in CRB 942. Data from the surveys will be entered into and stored in REDCap, accessed only by approved study personnel. Data will be downloaded and entered into a statistical software program for analysis. Audio files and transcripts from the post-intervention evaluation will be saved in Box and accessed only by approved study personnel.

8) Risks to Subjects*

The risks associated with participating in this study are those related to answering basic questions about demographic characteristics and smoking behaviors. Participants will be

Clinical Trials Registration #: NCT03999411

Date: 6/29/20

assured that their data and any audio recordings will be kept confidential and that they are free to not answer any questions.

9) Potential Benefits to Subjects*

Participants may be able to quit smoking through use of the intervention in the study.

10) Vulnerable Populations*

Those with HIV.

11) **Setting**

The study will take place at the Don Soffer Clinical Research Center, the Infectious Disease Research Unit, and Miami HIV community health centers.

12) Resources Available

The PI of the study, [name], has many years' experience in conducting tobacco control studies. [name] is also specialized in tobacco control. [name], the Director of the UM HIV Research Unit in the Department of Infectious Diseases, has expertise in HIV research, and will assist in coordinating recruitment.

13) Prior Approvals

Letters of Support from Drs. [name] at the UM HIV Registry and [name] from the Behavioral CFAR Core are attached.

14) Recruitment Methods

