We are collaborating with Drs. [name] (the Director of the UM HIV Registry) and [name] (Co-I; the Director of the UM HIV Research Unit) to recruit those who were identified as smokers in their database and have agreed to participate in future research (pls. see LOS from Drs. [name] and [name]). We will be provided with a list of potential participants including their names, contact information, smoking status, most recent HIV-1 viral load (VL), and ART regimen history (e.g., time since first starting ART, current prescription). This will include HIV Registry participants who have previously given consent to be contacted for future research studies. Eligible participants will be contacted by phone and invited to participate in the study. Those who are interested will be screened. Those who are eligibility will be scheduled to attend the orientation session. Those who are not eligible, or decline to participate will be encouraged to quit smoking and given a list of available resources. We will additionally recruit participants at HIV community health centers in Miami. The process here will be the same, where interested participants will be screened for eligibility and scheduled for an orientation session.

15) Local Number of Subjects

We will recruit up to 75 participants.

Clinical Trials Registration #: NCT03999411

Date: 6/29/20

16) Confidentiality

All participant data will be stored in a locked cabinet or in REDCap and accessed only by approved study personnel. Their name will be replaced with an ID number on their survey data and a key linking the two will be available only to approved research personnel and only for purposes of contacting them as needed in the study. Their name will not be associated with interview transcripts. Audio files from the interviews and electronic files such as verbal consents will be stored in Box and accessed only by approved study personnel.

17) Provisions to Protect the Privacy Interests of Subjects

Participants can be assured that the personal information they provide will only be seen by approved research staff and they will not be identified in any publication.

18) Consent Process

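### Sections 8, 16 and 17 do not cover the NRT, the named medication videos or the group orientation that section 5 prescribes, and the 3-month visit asks nothing about harms

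*Protocol*

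**What the plan says.** Section 8 (Risks to Subjects) gives one sentence on risk: "The risks associated with participating in this study are those related to answering basic questions about demographic characteristics and smoking behaviors". It then says that participants will be "assured that their data and any audio recordings will be kept confidential and that they are free to not answer any questions". Video is not mentioned, and neither is NRT.

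Section 16 (Confidentiality) states: "All participant data will be stored in a locked cabinet or in REDCap and accessed only by approved study personnel". Later in the same section, Box is added for interview audio and for electronic files such as verbal consents, again with access limited to study personnel. Section 17 promises that "the personal information they provide will only be seen by approved research staff".

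Sections 4 and 5 describe what participants will undergo:

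- **NRT.** Arms 1 and 2 each receive a 6-week supply, and Arm 3 receives everything in Arm 2. One exclusion entry in section 4 begins "Have contraindication to NRT (past month myocardial infarction" and goes on to serious arrhythmia, unstable angina and skin disease.
- **Video.** Arm 3 participants are told to light their face well, to "state their name, the date, and each medication as they take it, display their medication pills", and to repeat this at each intake. The app comes from an outside company (section 3). Study staff collect the adherence information through its web portal.
- **Group sessions.** Orientation and the taking of consent may be done individually or in groups.

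**The concern.** The sentence in section 8 is worded as a complete account: the risks *are* those of answering questions. Nothing marks it as a list of examples. A protocol that screens out people for whom NRT is contraindicated has already accepted that NRT carries some risk, so the two sections disagree. The same holds for disclosure. A recording that shows a face, gives a name and displays ART identifies its maker as a person with HIV, and a group session open only to people prescribed ART does much the same to those in the room.

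Two things are at stake. The first is participant protection: the sections that should describe risk and data handling leave out the most sensitive material the trial generates. The second is what the pilot can report. Aim 1 tests feasibility and acceptability ahead of a larger trial. If harms and unintended disclosure are never asked about, their absence from the results could be taken for their absence in fact.

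**Working it through.** No arithmetic decides this point, and the plan states no figure to reproduce. The check sets the sections side by side.

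**1. Risk statement against procedures**

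| Exposure | Where prescribed | Who | Covered in section 8? |
|---|---|---|---|
| Questionnaires | Section 5 | All arms | Yes |
| NRT, 6 weeks | Section 5; contraindications in section 4 | All arms, up to 75 people (section 15) | No |
| Named, face-visible ART videos | Section 5, Arm 3 | Arm 3 | No; the assurance names data and audio recordings |
| Orientation and consent in groups | Section 5 | Any arm, since there is an orientation video for each of the three | No |

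Of these four exposures, section 8 covers one. The allocation ratio is not stated. If it is equal (an assumption), Arm 3 has at most 75/3 = 25 people.

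**2. Storage statement against data flow**

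Section 16 names three places once its own later sentence is read in: cabinet, REDCap and Box. Box is limited there to audio and electronic files such as verbal consents. Section 7 (Data Management) has the same structure: paper in a cabinet, surveys in REDCap, audio and transcripts in Box. Arm 3 adherence information is reached through the app's portal, which is none of these. A statement about all participant data is therefore incomplete as written. Sections 7, 8, 16 and 17 name neither the videos, nor the portal, nor the company.

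**3. Access promise against data flow**

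Section 17 limits viewing to approved research staff. Section 5 says that study staff have full access to the portal. It does not say who else has access, or where the video files are kept. The promise may be true, but the protocol gives no basis for it where data pass through an outside company's system.

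**4. Consent against video**

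Section 18 plans a separate audio/video consent form and gives its purpose as recording the study visits. The medication videos, made away from the visits, are not named there.

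**5. Is any of this measured?**

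The 3-month assessment covers NRT use alongside smoking, extra NRT or cessation drugs, other tobacco, the repeated baseline scales, usability, three acceptability items, feasibility, smoking status and ART adherence. Deaths and withdrawals are recorded as categories of attrition. No item asks about adverse events or about unintended disclosure. The repeated withdrawal scale measures nicotine withdrawal and is not a record of NRT side effects. The app-feasibility calls take place in Arms 2 and 3 only, so the 3-month visit is the one follow-up assessment described for all arms.

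**The case against.** The strongest reply is that this is loose drafting in administrative sections. The consent pages are not in the file and may list NRT and video risks in full. The protocol has no safety objective and says nothing about adverse-event collection that could be wrong. It also contains protections: Arm 3 participants are told to find a private place to record, and written consent is planned.

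Part of this stands. What participants are actually told cannot be judged from section 8, and the missing harm questions are an omission, not a contradiction. They are therefore best treated as a consequence of the faulty risk statement and as an inexpensive improvement. The reply does not rescue the text itself. A fuller consent form would not correct section 8 or section 16, and would then disagree with them.

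Some stronger readings are tempting, and the documents do not support them:

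- *That vendor staff watch the videos, so that section 17 is false.* The protocol says only that study staff use the portal. The gap is an unsupported promise, not a proven breach.
- *That Box contradicts section 16.* Section 16 names Box and its access rule itself.
- *That reminder texts disclose HIV status.* Section 5 says that the texts will not mention HIV.
- *That the exposure can be sized by counting videos.* Dosing frequency, allocation ratio and actual use are not given, so any count would be idealised, and the point does not depend on one.

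**Conclusion.** The concern holds in a limited form. Section 8 is wrong as written, because it confines risk to answering questions while section 5 supplies NRT to every arm, has Arm 3 make identifiable ART videos and permits group orientation. Section 16 is wrong as written, because its account of all participant data leaves out the emocha data. Section 17 is unsupported for those same data, but is not shown to be false.

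The NRT omission concerns everyone enrolled, up to 75 people. The video and storage gap concerns Arm 3. These conclusions rest on the protocol text alone. The one inference is that attending a group session for this study suggests HIV status to the other attendees, which follows from the requirement that participants have been prescribed ART.

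The matter is one of participant protection and of what the pilot can say about harms. It does not bear on the efficacy comparison, on power or on any estimate. It is worth correcting before a larger trial builds on this one.

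**What to change.** 1. Reconcile section 8 with sections 4 and 5 by naming NRT-related adverse events and the risk of HIV-status disclosure through the medication videos and through group orientation.
2. Correct sections 16 and 17 to state where the emocha data, including the videos, are held and who can access them. Align section 7 with this. If the audio/video consent is meant to cover the medication videos, say so in section 18.
3. Add a short question on adverse events and one on unintended disclosure at the existing 3-month visit in all arms, and report the answers by arm. If similar questions are also put at the calls in Arms 2 and 3, keep those answers out of the between-arm comparison, since Arm 1 has no such calls.

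The cost is protocol and IRB rewording plus one or two questions at a visit already planned. No clinical rule on NRT is proposed.

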- 2. Only smoking cessation intervention (*Crave-to-Quit* app): This intervention is based on the theory of mindfulness-based cognitive therapy (MBCT) for relapse prevention.⁶⁴ The MBCT uses cognitive behavioral therapy methods in collaboration with MT techniques. Cognitive methods focuses on the development of personal coping strategies that target solving problems and changing unhelpful patterns in cognitions (e.g. thoughts, beliefs), behaviors, and emotional regulation.⁶⁵ MT focus on becoming aware of all incoming thoughts and feelings and accepting them, but not attaching or reacting to them.³⁶ This process is known as "Decentering" and aids in disengaging from self-criticism and rumination that can arise when reacting to negative thinking patterns.⁶⁶ Participants in this group will receive the UC for adherence to ART, one in-person orientation sessions, 6-week supplies of NRT, the "*Crave-to-Quit*" app, and two brief follow-up phone calls.

Orientation session. This session will occur 3 weeks before quit date and will last for 90 min. During the session, a research associate will explain the purpose, format, and procedures of the study. Participants will then watch a video that explains the specifics of their respective arm's study activities; there will be a different video for each of the 3 arms. After the video the research associate will go through the written informed consent, have the participant sign, and have the participant complete the baseline assessment. Then, participants will be instructed to download on their phone the "Crave-to-Quit" app and will receive a tutorial explaining the app content and features to troubleshoot any issues, followed by training on how to use the app and to practice MT techniques introduced in the app. Participants will be instructed to start using the app, and the app will assign a quit date within the next 3 weeks. Participants will receive 6 weeks of NRT, and will be instructed to start using the NRT at the quit date. Orientations and collection of consent may be conducted individually or in groups, according to participants' schedules.

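### Section 8 confines the study's risks to answering questions although every arm is supplied six weeks of NRT, and no contact as described asks directly about NRT reactions or adverse events

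*Protocol*

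**What the plan says.** **Risk and benefit.** Section 8 (Risks to Subjects) says: "The risks associated with participating in this study are those related to answering basic questions about demographic characteristics and smoking behaviors". It goes on only to promise confidentiality and the freedom to leave questions unanswered. Section 9 (Potential Benefits to Subjects) says: "Participants may be able to quit smoking through use of the intervention in the study".

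**What participants are given.** Section 5 (Procedures Involved) supplies NRT in each arm:
- Usual care receives "a brief advice to quit smoking, 6-week supplies of NRT, and self-help materials to quit smoking and adhere to ART".
- For arm 2 (Crave-to-Quit), the orientation paragraph says: "Participants will receive 6 weeks of NRT, and will be instructed to start using the NRT at the quit date".
- Arm 3 (Crave-to-Quit plus emocha) inherits the arm 2 package: "In addition to the intervention in the second group, participants in this group will be instructed" to use the second app as well.

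**What the protocol recognises elsewhere.** The exclusion list in section 4 contains "Have contraindication to NRT (past month myocardial infarction, history of serious arrhythmias/or unstable angina pectoris, dermatological disorder". The Background in section 3 describes quitting as a serious stressor associated with psychological stress and depression, and reports depression in people living with HIV at up to three times the general-population level.

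**Timing.** Of orientation, section 5 says: "This session will occur 3 weeks before quit date and will last for 90 min". It also says that "the app will assign a quit date within the next 3 weeks". The all-arm follow-up visit is 3 months after enrolment.

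**The concern.** The sentence in section 8 says what the risks are. It does not offer examples. Read as written, it excludes any risk from the supplied NRT or from the quit attempt that the study prompts. Yet the same protocol screens people out because NRT could harm them, and section 9 treats use of the intervention as a source of benefit.

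The described procedures follow the narrow statement. If the calls and visits are carried out as summarised, a non-fatal reaction to NRT, or another adverse event, comes to light only if the participant volunteers it. At stake are an accurate account of what participants are exposed to and systematic knowledge of reactions to a component that everyone is given.

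**Working it through.** No figure in the plan needs reproducing. The check sets the statements side by side, goes through every described contact after baseline, and works out one timeline.

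**Step 1: is section 8 accurate?** NRT is supplied in 3 of 3 arms (section 5), to up to 75 people (section 15). Section 4 names cardiac and dermatological contraindications to it. Section 3 names the mood effects of quitting. Section 8 mentions none of these, so it is wrong as written.

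**Step 2: does any described contact ask about reactions or adverse events?**

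| Contact (section 5) | Arms | Described content | Asks directly? |
|---|---|---|---|
| Call 1, the day before the quit date | 2, 3 | Reminder, support, System Usability Scale (SUS) | No |
| Call 2, 6 weeks after the quit date | 2, 3 | Progress, support, scheduling, SUS | No |
| Weekly calls, or daily calls for six participants, for 3 weeks | 2, 3 | Mindfulness practice, use and opinion of the app | No |
| Text messages | Not specified | Reminders | No |
| emocha videos | 3 | Taking of antiretroviral doses | No |
| 3-month visit | All | NRT use, other cessation drugs, smoking, repeat of the baseline scales, usability and acceptability | No |
| Aim 2 interview | 2, 3 | Acceptability, helpfulness, refinement | No |

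The count is 0 of 7. Deaths and withdrawals are recorded, but only as categories of attrition.

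**Step 3: what does the 3-month visit capture indirectly?** It repeats all baseline assessments except demographics. That includes quality of life, the 10-item CES-D and the 15-item withdrawal scale, and the visit also asks about NRT use. These describe mood and withdrawal around the visit, and whether NRT was used. They do not record a reaction to NRT, and a mood change that has resolved by then can be missed.

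**Step 4: when does that visit fall relative to NRT use in arms 2 and 3?** Inputs:
- 3 months = 91 days = 91/7 = 13 weeks after enrolment.
- Enrolment is taken as the orientation date (assumption).
- The quit date is 3 weeks after orientation.
- NRT starts on the quit date and lasts 6 weeks.

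Results:
- NRT starts at week 3 and the supply ends at week 3 + 6 = 9.
- Supply end to visit: 13 − 9 = 4 weeks.
- NRT start to visit: 13 − 3 = 10 weeks.
- NRT start to call 2: 6 weeks, because that call is itself set at 6 weeks after the quit date.

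Usual care cannot be placed on this timeline. Its quit date is not stated, and no call is described for it.

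**The case against.** **Silence in summaries.** The protocol gives one-line accounts of the calls. Scripts, visit forms and consent pages are not shown, and a call that reviews progress may bring out side effects. This stands as a limit: the count of zero applies to the procedures as written. It does not rescue section 8. A fuller consent form would conflict with that section and would not correct it.

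**Indirect information exists.** A reader might infer that the pilot will yield no tolerability information at all. The documents do not support that. NRT use, additional NRT and other cessation drugs are recorded at 3 months in all arms, so under-use or switching could hint at poor tolerability. Quality of life, CES-D and withdrawal are measured, attrition is classified, and the interviews are semi-structured. What is missing is a direct question.

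**The trial's aims are untouched.** The pilot concerns the two apps, and NRT is background treatment supplied for the same 6 weeks in every arm. A reader might infer that the comparison between arms is compromised. Nothing in the protocol supports that.

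**Risk is partly controlled.** Contraindications, pregnancy and current psychiatric treatment are exclusions. Participants must already be interested in a quit attempt within 30 days, so the stress of quitting is not wholly added by the study. This lowers the expected frequency of harm, but it does not make the risk statement accurate.

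**Longer gaps.** Because the app assigns a date at some point within 3 weeks, a reader might take a quit date on the day of orientation and obtain gaps of 13 − 6 = 7 and 13 − 0 = 13 weeks. That date does not fit. Call 1 comes the day before the quit date and includes the SUS for an app downloaded only at orientation. The protocol also places orientation 3 weeks before the quit date.

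**Usual care.** The orientation paragraph mentions videos for all three arms, and the feasibility measures count calls received in each arm. So a usual-care call is not ruled out; none is described.

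**Conclusion.** The point holds as an error of risk disclosure and participant safety. Section 8 is contradicted by sections 3, 4 and 5 of the same protocol. Up to 75 participants in all three arms are supplied NRT, and 0 of 7 described kinds of contact ask directly about reactions or adverse events. In the app arms, the only assessment visit after baseline comes about 4 weeks after the supply ends and 10 weeks after it starts.

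The intervals rest on two assumptions: enrolment dated from orientation, and a quit date 3 weeks later. They are recall intervals and do not measure harm. No event rate is assumed, and the documents give none. The finding on contacts is confined to the procedures as described. A statistical analysis plan would not cure either part, since the risk statement and the content of contacts belong to the protocol.

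**What to change.** 1. Rewrite section 8 to name reactions to NRT and the mood and withdrawal effects of a quit attempt.
2. Add one identically worded question on adverse events and NRT tolerability, covering the time since enrolment, to the existing 3-month visit in all arms, and report it by arm. Ask it also at the 6-week call already planned in arms 2 and 3. Report those answers separately, because usual care has no described call and pooling would favour detection in the app arms.
3. Have an existing investigator review any serious event and any NRT stopped because of a reaction.

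The cost is a short amendment, a few minutes per contact and brief review time, with no new visit or staff. Two limits remain. Recall at the 3-month visit is about 10 weeks from the start of NRT, against 6 weeks at the call. Real-time detection in usual care stays limited.
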